#### **3.5.2.** Laboratory Data

Blood and urine samples will be collected at the time points identified in the protocol for clinical safety laboratory tests and exploratory biomarkers (Table 2). Unscheduled clinical laboratory tests may be performed at any time during the study to assess any perceived safety concerns.

Laboratory Testing Profile	Tests Included
Laboratory Tests Required at Screening Only	QuantiFERON®-TB Gold In-Tube, hepatitis C virus antibody (HCV Ab), hepatitis C virus RNA (HCV RNA) a , hepatitis B surface antigen (HBsAg), hepatitis B core antibody (HBcAb), hepatitis B surface antibody (HBsAb) b , HIV-1/HIV-2 antibody screen, Prothrombin time (PT/INR) e ; FSH (optional for post- menopausal women only)
Hematology	Hemoglobin, hematocrit, RBC, RBC morphology, reticulocyte (abs); White blood cell (WBC) count and differential, [neutrophils (%, abs), lymphocytes (%, abs), monocytes (%, abs), eosinophils (%, abs), basophils (%, abs)], platelets Hemaglobin A1c (HbA1c)
Chemistry Panel	Urea nitrogen, creatinine, glucose, calcium, sodium, potassium, bicarbonate, chloride, total protein, total bilirubin, direct bilirubin, indirect bilirubin, alanine transaminase (ALT), aspartate transaminase (AST), alkaline phosphatase, gamma-glutamyl transferase (GGT), albumin, creatine kinase (CK)
	Rheumatoid Factor (RF), Cyclic Citrullinated Peptide Antibody (CCP)
Lipid Panel	Fasting total cholesterol, HDL, LDL, triglyceride; apolipoprotein A-1, B and other lipoprotein tests potentially including particle size measurements
Urinalysis	Specific gravity, pH, protein, glucose, ketones, blood, leukocyte esterase. Urine HCG pregnancy testing for women of childbearing potential.
	Microscopy and/or culture to be performed if clinically indicated or if urinalysis results positive (blood, protein or leukocyte esterase/WBC)
Acute Phase Reactants	C-reactive protein (CRP, tested centrally)

#### Table 2 Clinical Laboratory Testing

a Only subjects who are HCV Ab positive should be reflex tested for HCV RNA.

b Only subjects who are HBsAg and HBcAb+ should be reflex tested for HBsAb.

c All subjects will be screened for normal prothrombin time (PT/INR). PT should also be evaluated to rule out acute hepatic injury in cases of hepatic enzyme elevations.

#### 4. ANALYSIS SETS

Below is a description of the analysis sets defined for this study. Note that subjects who are screened but not randomized will appear on the subject evaluation table and that subjects who are randomized but not treated will appear on the subject evaluation table; this will the extent of how much data for these subjects will be reported. If a subject is treated but not randomized, then the subject will be excluded from any analyses. A narrative will be provided for this subject in the clinical study report (CSR).

Data for all subjects will be assessed to determine if subjects meet the criteria for inclusion in each analysis population prior to unblinding and releasing the database and classifications will be documented per standard operating procedures.

#### 4.1. Full Analysis Set

The Full Analysis Set (FAS) will include all subjects randomized and who have received at least one dose of randomized study drug (tofacitinib or placebo). Subjects will be analyzed in the treatment groups as they are randomized regardless of what treatment they received. FAS is the primary patient population for the primary endpoint.

Continuous and ordered-categorical (analyzed as continuous) endpoints for which change or percent change from baseline is the measure to be analyzed, would require that a subject have a baseline value and at least one post-baseline value to be included in the FAS for that endpoint. It is anticipated that there should be little bias due to excluding subjects with no baseline since the missingness mechanism is likely to be missing completely at random (MCAR) (Rubin, 1987). Excluding a subject with no post-baseline would likely cause a more favorable estimate of the mean change from baseline for that endpoint for the treatment group in which that subject was assigned (since subjects not responding are more likely to drop out prior to a post-baseline measure than those who are responding). However, it is anticipated that very few subjects will be excluded for this reason minimizing any potential bias.

#### 4.2. Per Protocol Analysis Set

The Per Protocol (PP) analysis set will be a subset of FAS and will exclude all subjects who had a protocol deviation thought to have a material impact on the primary efficacy analysis. The PP analysis set will be used in the PP efficacy analysis for the primary endpoint of ACR50 at Month 3.

The following sections describe protocol deviations that will lead to subject exclusion from the PP analysis set. It is possible that unexpected deviations will arise, becoming known only after the study has been active for a long period of time; hence more deviations may be added to the list at a later date. As of this writing, the protocol deviations that will define the PP analysis set can all be found in Section 4.2.1 and Section 4.2.2 below.

#### 4.2.1. Protocol Deviations Assessed Prior to Randomization

- Subjects who failed to meet the Classification Criteria for Psoriatic Arthritis (CASPAR) diagnostic criteria for PsA at screening. The PsA diagnosis at screening will be recorded on the PRIMARY DIAGNOSIS CRF where PSORIATIC ARTHRITIS is pre-filled. Subjects who did not have the CRF filled out will be considered as having this exclusion criteria met.
- Subjects who had < 3 tender/painful joints on motion out of 68 joints assessed or < 3 swollen joints out of 66 joints assessed at either screening or baseline (i.e., Day 1 Pre-dose). The "JOINT SWELLING AND TENDERNESS 66/68 JOINT COUNT ASSESSMENT" CRF will be used to check this condition.

- Subjects who failed to meet the criterion of "an inadequate response (IR) to at least one csDMARD due to lack of efficacy (LOE) and/or toxicity/lack of tolerance (due to treatment-related AE)". csDMARD-IR is defined as those csDMARDs that were discontinued due to AE, LOE, or both AE/LOE on or prior to Day 1, or a csDMARD that was started prior to Day 1, but was not discontinued and continued beyond Day 1 regardless of csDMARD dose change.
- Subjects who met the exclusion criterion of "history of or current autoimmune rheumatic disease or rheumatic inflammatory disease other than PsA". The "SIGNIFICANT MEDICAL HISTORY" CRF and anti-CCP tested at baseline will be used to check this condition. Subjects who were considered to have current autoimmune rheumatic disease or rheumatic inflammatory disease other than PsA by the investigator and/or the Sponsor will also be excluded.

#### 4.2.2. Protocol Deviations Assessed Post-Randomization

- Subject who was randomized but took or received incorrect treatment other than the randomized treatment for the entire duration from baseline through Month 3. This will be checked manually since there is no CRF for this condition.
- Subject who had < 80% compliance with tablet on 2 consecutive visits for the period from baseline through Month 3. The study treatment compliances will be calculated based on "ORAL DOSING" CRF. Both randomized treatments (i.e., tofacitinib and placebo) will be taken into account.
- Subject who received rescue medication for PsA on the preceding day or the same day of the primary endpoint assessment at Month 3. The rescue medication is recorded on "PRIOR AND CONCOMITANT MEDICATIONS : OTHER" CRF in the "RESCUE MEDICATIONS" category.

A list of DMARDs is given in Appendix 3 Section 17. The list will be reviewed and updated as new versions of MedDRA dictionary become effective and any updates will be maintained in a programming plan.

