### 5.8. Concomitant Medication(s)

It is important to be aware of, and document, **all** concomitant medications including: prescription, non-prescription (ie, over-the-counter) and herbal medications.

A subject who is receiving an allowed concomitant medication for any reason must be on a locally-approved medication and dose that is considered standard-of-care for the treated indication, and this must be documented in the case report form. Subjects are not allowed on any other investigational drug during the study.

It is recommended that subjects avoid changing non-prohibited prescription or non-prescription drugs, vitamins, and dietary supplements within 7 days or 5 half-lives (whichever is longer) prior to the first dose of study medication and prior to study visits unless otherwise noted below, throughout the study.

Medications that are taken in the Screening period (after informed consent is obtained and before the first dose of study drug) will be documented as prior medications. Medications taken after the first dose of study drug has been administered will be documented as concomitant medications. All concomitant medications taken during the study must be recorded in the study records with indication (as appropriate), daily dose, administration route and start and stop dates of administration. Subjects will be queried about concomitant medications at each study visit.

Minimum guidelines for folate supplementation during study: Subjects on methotrexate **must** receive folate supplementation according to local methotrexate label guidelines and standard of care. A minimum of 5 mg weekly based on folic acid should be given unless local guidelines or standard of care state otherwise.

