# 5.9. Rescue Therapy

The only medications that are allowed for rescue are listed in Appendix 5.

Increases of acetaminophen/paracetamol and opioids are allowable as rescue medication for no more than 10 consecutive days. Acetaminophen/paracetamol may be added or increased to a maximum of 2.6 gm/day. Opioids may be added or increased to a maximum potency equivalent of 30 mg of orally-administered morphine. Acetaminophen/paracetamol is not permitted as a part of combination products such as over-the-counter "cold remedies" or in combination with opioids if the total acetaminophen/paracetamol dose will exceed 2.6 gm/day.

Subjects who require rescue for more than 10 consecutive days should be discontinued from the study. There is no limit to the duration of nonconsecutive use of rescue medications. In addition, subjects may not be dosed with rescue medication during the 24 hours prior to a study visit. Baseline stable use acetaminophen/paracetamol or opioids should NOT be discontinued in advance of study visits.

A maximum of 40 mg methylprednisolone or equivalent of intraarticular corticosteroids will be allowed as rescue medication at or after the Month 3 visit; intraarticular corticosteroid injections should not be performed within the 4 weeks prior to a study visit. The total allowed intraarticular corticosteroid dose may be divided into separate injections (eg, 20 mg, 20 mg). Intra-articular hyaluronate sodium injections may be administered for indications in accordance with the local label at or after the Month 3 visit in no more than two joints. If performed at Month 3 visit, intra-articular injections must be given after the assessments are completed.

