#### For subjects who ARE on stable, background opioid therapy:

- They may NOT add a second opioid agent for rescue;
- If their background medication is 1 of the 3 listed above, they may, within the above maximum total dosage limits, increase the dosage for up to 10 consecutive days for rescue purposes;
- If their background medication is a short-acting (half-life <5 hrs, Appendix 4) opioid that is not one of those listed above, they may increase the dosage for up to 10 consecutive days (up to a total daily dose which must not exceed the potency equivalent of 30 mg of orally-administered morphine [Appendix 4]) for rescue purposes;
- Sustained release opioid formulations (eg, OxyContin®, MS Contin®) and opioids with half lives greater than 5 hours (eg, methadone, propoxyphene) may NOT be USED for rescue medication.

Sustained release opioid formulations (eg, OxyContin®, MS Contin®) and opioids with half lives greater than 5 hours (eg, methadone, propoxyphene; see also Appendix 4) may NOT be INCREASED for rescue purposes.

Intravenous or intramuscular corticosteroids, biologic response modifiers and DMARDs, other than methotrexate and sulfasalazine, are not allowed during this study. Intra-articular corticosteroids may be given at or after the Month 3 visit in no more than two joints, in a cumulative dose of no more than 40 mg methylprednisolone or its equivalent in any 6 month study period. The total allowed intraarticular corticosteroid dose may be divided into separate injections (eg, 20 mg, 20 mg). Intra-articular hyaluronate sodium injections may be administered for indications in accordance with the local label at or after the Month 3 visit, intra-articular injections must be given after assessments are completed. Intra-articular corticosteroids should not be administered within 4 weeks prior to a study visit.

Acetaminophen/paracetamol is not permitted as a part of combination products such as over-the-counter "cold remedies" or in combination with opioids if the acetaminophen/paracetamol dose will exceed 2.6 gm/day. Subjects who require rescue for more than 10 consecutive days should be discontinued from the trial. In addition, subjects should not be dosed with rescue acetaminophen/paracetamol or opioids within 24 hours prior to a study visit. Baseline stable acetaminophen/paracetamol or opioids should NOT be discontinued in advance of study visits.

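### The per-protocol rule on Month 3 rescue also excludes subjects whose rescue came after the assessments, which the protocol does not prohibit

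*SAP*

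**What the plan says.** SAP 4.2 makes the PP set a subset of the FAS that "will exclude all subjects who had a protocol deviation thought to have a material impact on the primary efficacy analysis". SAP 4.2.2 then lists the post-randomization deviations that lead to exclusion, and the last is: "Subject who received rescue medication for PsA on the preceding day or the same day of the primary endpoint assessment at Month 3". The check uses the rescue category of the other-medications CRF.

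Protocol 5.9 states the restriction as "subjects may not be dosed with rescue medication during the 24 hours prior to a study visit". On injections it says: "A maximum of 40 mg methylprednisolone or equivalent of intraarticular corticosteroids will be allowed as rescue medication at or after the Month 3 visit". On order it adds: "If performed at Month 3 visit, intra-articular injections must be given after the assessments are completed". Appendix 5 gives the same starting point: "Intra-articular corticosteroids may be given at or after the Month 3 visit in no more than two joints".

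For concomitant medication, Protocol 5.8 asks for the indication and "daily dose, administration route and start and stop dates of administration". It does not list a clock time.

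**The concern.** The PP set is meant to show the effect without deviations that matter to the primary endpoint. Rescue given after the Month 3 assessments is not a deviation under the protocol, yet the bullet treats it as one. Month 3 is also the first visit at which intra-articular rescue is allowed, so same-day rescue there is foreseeable.

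Need for rescue just after an assessment plausibly depends on how the subject is doing. Membership of the PP set would then depend partly on something downstream of the outcome. Supportive Analysis 1 reports a difference, a confidence interval and a p-value from that set, and a reader would take it as the result in subjects who followed the protocol.

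**Working it through.** **1. The two rules side by side**

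| Rescue | Protocol | SAP 4.2.2 |
|---|---|---|
| Oral, Month 3 day, before assessment | restricted | excluded |
| Oral, Month 3 day, after assessment | not restricted, within the other limits | excluded |
| Injection at the Month 3 visit, after assessments | allowed, in that order | excluded, if entered as rescue |
| Oral, day before, within 24 hours of the visit | restricted | excluded |
| Oral, day before, more than 24 hours earlier (08:00 before an 11:00 visit: 27 hours) | not restricted | excluded |

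Rows 1 and 4 agree. Rows 2 and 3 are the point. Row 5 is a side effect of working with dates. SAP 4.2 foresees adding deviations to the list; it does not mention relaxing one.

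**2. Planning figures**

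Inputs from Protocol 9.1: 136 and 68 subjects, placebo rate 9.5%, difference 18.5 points, hence 28.0% on tofacitinib. With the unpooled variance of SAP 5.2.1.1:

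- SE = √(0.28×0.72/136 + 0.095×0.905/68) = 0.0524.
- Z = 0.185/0.0524 = 3.53; 95% CI 18.5 ± 1.96×5.24 = 8.2 to 28.8 points.
- Power = Φ(3.53 − 1.96) = 94.2%. With the 11 COVID-19 missing values set to non-response in proportion (26.5% vs 9.0%) it is 92.6%.

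The stated power of at least 90% is met on this formula. It concerns the FAS and does not depend on the PP rule.

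**3. What the exclusion could do**

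The shares below are assumptions, because the documents give no same-day rescue rate. Suppose a share r of an arm is removed, all of them non-responders, with no other PP exclusions. The rate p becomes p/(1 − r), so the difference is 28.0/(1 − r_t) − 9.5/(1 − r_c).

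| Removed, placebo / tofacitinib | Rates, tofacitinib vs placebo | Difference (95% CI) | Z |
|---|---|---|---|
| 0% / 0% | 28.0 vs 9.5 | 18.5 (8.2 to 28.8) | 3.53 |
| 5% / 5% | 29.5 vs 10.0 | 19.5 (8.7 to 30.2) | 3.55 |
| 10% / 5% | 29.5 vs 10.6 | 18.9 (7.9 to 29.9) | 3.37 |
| 10% / 2% | 28.6 vs 10.6 | 18.0 (7.1 to 28.9) | 3.25 |
| 15% / 5% | 29.5 vs 11.2 | 18.3 (7.0 to 29.6) | 3.17 |
| 20% / 5% | 29.5 vs 11.9 | 17.6 (5.9 to 29.2) | 2.96 |
| 5% / 10% | 31.1 vs 10.0 | 21.1 (10.1 to 32.1) | 3.76 |

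The difference is unchanged when 28.0·r_t/(1 − r_t) = 9.5·r_c/(1 − r_c), that is, when the odds of removal on placebo are 28.0/9.5 = 2.95 times those on tofacitinib. At r_t = 5% this is r_c = 13.4%. Below that the PP difference rises; above it, it falls.

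**4. The injected-joint rule**

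SAP Appendix 3 Section 9 sets an injected joint to Present from the date of injection, whatever was recorded; Section 10 treats tender joints similarly. A joint assessed at Month 3 and injected later that day is therefore overwritten. If it was already recorded as Present, nothing changes. If not, the count rises, and ACR50 can only move from response to non-response. Example: 4 swollen joints at baseline and 2 at Month 3 is a 50% improvement. If one injected joint was recorded as not swollen, the derived count is 3 and the improvement (4 − 3)/4 = 25%.

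**The case against.** The strongest defence is practical. If the CRF holds only dates, a preceding-or-same-day rule is the natural date version of a 24-hour restriction, and it errs towards excluding doubtful cases. A strict 24-hour rule may not be programmable for oral doses, and blinded review cannot recover a time that nobody recorded. This stands. It is why the day-before case is not a separate defect and why a date-based default should remain. It does not cover injections, whose route is recorded and whose order the protocol fixes.

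A second defence is that subjects injected on the day have derived joint counts that may be overwritten, so leaving them out of the PP set has a rationale. A reader might infer that rescue after the assessments cannot have touched the ACR50 result. For injections the documents do not support that, because of Appendix 3 Section 9. Also, Protocol 6.2.5 lets blood be taken up to 48 hours after the visit, so the CRP sample could follow same-day rescue. But the overwriting is a derivation problem that enters ACR50 in the FAS as well. Dropping compliant subjects from the PP set does not solve it.

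Third, SAP Section 4 requires set membership to be decided before unblinding, and SAP 4.2 speaks of material deviations, so the review would have grounds to keep such subjects. That is fair, but the bullet as written points the other way.

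**Conclusion.** The mismatch is real and rests on the text alone: followed literally, SAP 4.2.2 removes subjects who complied with the protocol, on an event after the outcome. That such rescue relates to response is plausible, not documented.

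The consequence is limited. The bullet affects only Supportive Analysis 1. A reader might infer that the primary result or its power is biased by it. The documents do not support this, since the primary analysis and the decision rule use the FAS. A reader might also infer that the rule favours tofacitinib. That is not supported either: under the assumptions shown, the difference moves by −0.9 to +2.6 points, the sign depends on the unknown balance between arms, and Z stays between 2.96 and 3.76. These figures illustrate scale and predict nothing.

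The injected-joint date rule is a neighbouring matter of wider reach, because it enters the derived Month 3 joint counts wherever ACR50 is used. How often it would change a response cannot be told from the documents.

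**What to change.** Before unblinding, reword the SAP 4.2.2 bullet along these lines:

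*Subject with rescue for PsA that breaches the protocol's pre-visit restriction for the Month 3 visit. Rescue given after the Month 3 assessments does not exclude. An intra-articular injection dated on the Month 3 visit day, identified by route and date, is taken to follow the assessments, as the protocol requires. For oral rescue dated on that day or the day before, order is settled from source in the blinded classification under SAP Section 4. If it cannot be established, the subject is excluded.*

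The bullet should cite the restriction exactly: Protocol 5.9 states it without exception, whereas the end of Appendix 5 allows for medical necessity. The sponsor should reconcile the two passages.

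In Appendix 3 Sections 9 and 10, apply the injected-joint rule only to assessments made after the injection, so that a joint assessed before a same-day Month 3 injection keeps its recorded value.

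Cost: a few SAP sentences and some blinded manual review. Clock times may not have been collected, so some oral cases will stay excluded by default. Because the Appendix 3 change touches the derivation of the primary endpoint, the sponsor should record whether it counts as a major modification under SAP Section 2, which would call for a protocol amendment. No rescue rule changes.

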#### 4.3. Safety Analysis Set

The safety analysis set (SAFETY) will include all subjects who received at least one dose of the study drug (tofacitinib or placebo). Subjects will be classified according to the actual study treatment received.

#### 4.4. Other Analysis Sets

#### 4.4.1. Endpoint Specific Analysis Sets

Subjects will be excluded from FAS for analyzing a specific endpoint if the criterion for inclusion is not met for the endpoint as described in Table 3.

Instrument/Endpoint	Inclusion	Rationale
HAQ-DI responder (decrease $\Delta$ HAQ-DI $\geq$ 0.30)	Include subjects with baseline HAQ-DI $\geq 0.30$	Restrict baseline HAQ-DI to $\geq 0.30$ to allow room for response.
HAQ-DI responder (decrease $\Delta$ HAQ-DI $\geq$ 0.35)	Include subjects with baseline HAQ-DI $\geq 0.35$	Restrict baseline HAQ-DI to $\geq 0.35$ to allow room for response.
ΔPGA-PsO	Include subjects with baseline PGA-PsO > 0	Baseline $PGA-PsO = 0$ means no PsO disease at baseline.
PGA-PsO responder (PGA-PsO = 0 or 1 and decrease $\triangle$ PGA-PsO $\geq$ 2)	Include subjects with baseline PGA-PsO $\geq 2$	Restrict baseline PGA-PsO to $\geq 2$ to allow room for response.
PASI75	Include subjects with baseline BSA $\ge$ 3% and baseline PASI $>$ 0	PASI is not assessed if baseline BSA < 3% per the study protocol; PASI = 0 means absence of psoriasis as measured by PASI.
ΔDSS	Include subjects with baseline DSS > 0	Baseline DSS = 0 means absence of dactylitis. Dactylitis is not an enrollment criterion so it is expected that only a subset of the subjects will have dactylitis at baseline.
Resolution of dactylitis (DSS = 0)	Include subjects with baseline DSS > 0	Baseline DSS = 0 means absence of dactylitis. Dactylitis is not an enrollment criterion so it is expected that only a subset of the subjects will have dactylitis at baseline.

